Appendix 4 - Tables

Table 4 – Schedule of Study Procedures

Protocol-planned procedures and forms to be completed	Pre-screening and Screening	Baseline	e Treatment period										End-of-Treatment Visit until End-of- Hospitalisation Visit			Follow-up period (months)
Timepoint	D-15 to D-1	D-4 to D- 1	D1	D2	D3	D4	D5	D6	D7	D8	D9	D10	D11	D12	D13-D18	Week 9 ³ 3 – 6 – 12 – 18 -24 months
Detection of parasite in blood and/or lymph	Х												х			х
Lumbar puncture (parasite and white blood cells in CSF)	x												х			x ¹
Informed consent (before any additional medicines or study-specific procedures)	×	Check														
Pretreatment of helminthiasis (+ 3-day recovery period)	x															
Rapid diagnostic test and/or thick blood smear for malaria	Х															
Pretreatment of malaria if necessary (+ 3-day recovery period)	x															
Karnofsky score	Х	Check														х
Safety ECG	Х	Check														
Safety ECG (fexinidazole group only)				х	х	х										
Urine pregnancy test		х													х	x (only at 3 months)
Inclusion and exclusion criteria	Х	х														
Randomisation		х														
Demographic data	Х															
Medical history	Х															х
Signs and symptoms of HAT		х													х	х
Vital signs	Х	х					х			х			х		х	х
Physical examination		х					х			х			х		х	х
Neurological examination		х					х			х			х		х	х
Haematology and biochemistry	Х	х					х			х			х			x (only at Week 9)
Haematocrit ²	Х															
Urine analysis	Х	х											х			

¹ Except for 3-month follow-up visit unless the patient presents with clinical symptoms or signs of HAT.

² Only for patients at sites where PK sampling is performed.

³ Only at Week 9 after D1, perform sampling for haematology and biochemistry, physical examination and neurological examination.

Protocol-planned procedures and forms to be completed	Pre- screening and Screening	Baseline		Treatment period						End-of-Treatment Visit until End-of-Hospitalisation Visit			Follow-up period (months)			
Timepoint	D-15 to D-1	D-4 to D-1	D1	D2	D3	D4	D5	D6	D7	D8	D9	D10	D11 (EOT)	D12	D13-D18	Week 9 3 – 6 – 12 – 18 -24 months
Triplicate ECGs –fexinidazole group		x				x D4H4 D4H23						x D10H2-H3				
Triplicate ECGs – NECT group		x							x D7H2- H3			x D10H2-H3				
Administration of fexinidazole			х	х	х	х	х	х	х	х	х	х				
Administration of NECT			х	х	х	х	х	х	х	х	х	х				
Treatment-related adverse events			х	х	х	х	х	х	х	х	х	х	х	х	х	
Treatment-related serious adverse events			x	x	x	x	х	x	х	x	x	x	х	x	x	x (up to 24 months)
Recording of concomitant medication	x	х	х	х	х	х	х	х	х	х	х	х	х	х	х	
Dry blood spot sampling										x D8 H3.15	x D9H3	x D10H3 D10H7.15	x D10H24	x D10H48		
CSF sampling													x D10H24			

Table 5 – Overview of Protocol-planned Analyses

Analysis	Patients (n) (ITT)	Timepoint	Efficacy endpoints	Stopping Rules \blacklozenge π : actual responder rate p: observed responder rate	Power Chances of stopping the study due to actual responder rate (exact power)	Chances of stopping the study unduly (exact probabilities)
Futility analysis 1 Performed if the number of responders is ≤ 26/30 patients	20 (fexi) 10 (NECT)	End-of- Treatment Visit	Responder = no evidence of trypanosomes* at end of treatment	Unacceptable limit: π fexi < 95% = worse than melarsoprol (published results on responder rate at end of treatment p= 95.2% for melarsoprol; n= 6840) Stop if p fexi ≤ 80% Or if the number of responders is ≤16 out of 20 patients	58.9% if π fexi = 80% 77.5% if π fexi = 75% 89.3% if π fexi = 70%	1.59% if π fexi = 95% 0.0043% if π fexi = π NECT = 99%
Futility analysis 2 Performed if the number of responders is ≤ 97/105 patients	70 (fexi) 35(NECT)	End-of- Treatment Visit	Responder = no evidence of trypanosomes* at end of treatment	Unacceptable limit: π fexi < 95% (historical responder rate for melarsoprol) with π NECT \ge 99% (expectation for NECT and eflornithine) Or if the difference between the responder rates is > 4% in favour of NECT: $\pi_{NECT} - \pi_{Fexi} > 4\%$ Stop if Rule 1: p fexi $\le 88.57\%$ ($\le 62/70$) and p NECT $\ge 94.29\%$ ($\ge 33/35$) OR Rule 2: p NECT - p Fexi $\ge 15.7\%$ and p NECT $< 94.2\%$ ($< 33/35$) (Rule 2: modified Blackwelder test)	Rule 1 40.1% if π fexi = 90% 84.3% if π fexi = 85% 98.0% if π fexi = 80% Rule 2 29% if π fexi = 85% and π NECT = 98% 63.2% if π fexi = 80% and π NECT = 98%	Rule 1 2.33% if π fexi = 95% 0.0000% (if π fexi = 99%) Rule 2 0.08% (if π fexi = 95% and π NECT = 98%) 0.02% (if π fexi = 95% and π NECT = 97%) Note: the probability of applying Rule 2 is low (0.5%) if NECT \approx efformithine

Analysis	Patients (n) (ITT)	Timepoint	Efficacy endpoints	Stopping Rules \blacklozenge π : actual responder rate p: observed responder rate	Power Chances of stopping the study due to actual responder rate (exact power)	Chances of stopping the study unduly (exact probabilities)

Analysis	Patients (n) (ITT)	Timepoint	Efficacy endpoints	Stopping Rules \blacklozenge π : actual responder rate p: observed responder rate	Power Chances of stopping the study due to actual responder rate (exact power)	Chances of stopping the study unduly (exact probabilities)
Futility analysis 5 Performed if the number of responders (favourable outcome) is ≤ 79/105 patients	70 (Fexi) 35 (NECT)	12 months after End of Treatment	Responder at 12 months = no evidence of trypanosomes and CSF WBC ≤ 20/µL OR CSF WBC > 20 and <50/µL and reduced in relation to previous value(s) #	$ \begin{aligned} \pi \ \mbox{Fexi} &< 75\% \ (\mbox{worse that melarsoprol} \\ \mbox{at 12 months}) \ \mbox{and } \pi \ \mbox{NECT} \ge 95\% \ \mbox{OR} \\ \pi \ \mbox{NECT} - \pi \ \mbox{Fexi} > 13\% \ \mbox{(worse than} \\ \mbox{the limit of unacceptable difference)} \\ \mbox{(responder rate at 12 months =} \\ \mbox{74.84\% for melarsoprol and } 90.3\% \\ \mbox{for eflornithine})^{\mbox{a}} \\ \mbox{for eflornithine})^{\mbox{a}} \\ \mbox{Stop if} \\ \mbox{Rule 1: p fexi} \le 62.9\% \ \mbox{($\le 44/70$) and} \\ \mbox{p NECT} \ge 85.7\% \ \mbox{($\ge 30/35$)} \\ \mbox{OR Rule 2: p NECT} - p \ \mbox{Fexi} \ge \\ \mbox{25.71\% and p NECT} < 85.7\% \end{aligned} $	Rule 1 12.1% if π Fexi = 70% 39.7% if π Fexi = 65% 72.7% if π Fexi = 60% Rule 2 33.4% if π fexi = 70% and π NECT = 95% 58.8% if π fexi = 65% and π NECT = 95%	Rule 1: 0.000% if π fexi = 90% Rule 2 0.000% (if π fexi = 90% and π NECT = 95%) 0.01% (if π fexi = 85% and π NECT = 95%)
Interim analysis	195 at 12 months	12 months after End of Treatment	Primary endpoint at 12 months	None	NA	NA
Final analysis	390 at 18 months	18 months	Primary endpoint	None		

• Stopping rules: $\pi < x\%$ means that the observed responder rate is significantly lower than x%; $\pi = x\%$ means that the responder rate is compatible with an actual rate of f x%. π NECT - π Fexi > 2% means that the observed difference between the responder rates is significantly higher than z% in favour of NECT.

* "Responder" at the end of treatment (EOT) is defined as patient alive with no evidence of trypanosomes in any bodily fluid, i.e. blood, lymph or CSF, 24 hours after the end of treatment.

¤ Humbelin, 2006.

** The choice of the limit for the difference is based on the rounded difference between melarsoprol and effornithine instead of NECT because more data are available on effornithine (n = 748). Consequently, the stopping rules are defined as a difference with regard to NECT significantly larger, i.e. worse, than the difference between melarsoprol and effornithine. x = See below time course of the response for melarsoprol, effornithine and NECT.

Δ "Responder" at 3 months is defined as patient alive with no evidence of trypanosomes in any bodily fluid, i.e. blood, lymph or CSF or no neurological signs or symptoms requiring rescue treatment.

"Favourable outcome" at 6 and 12 months is defined as patient alive with no evidence of trypanosomes in any bodily fluid and CSF WBC $\leq 20/\mu$ L CSF, or CSF WBC > 20 and $< 50/\mu$ L and reduced in relation to previous value(s). Relapse at 6 and 12 months is defined as evidence of trypanosomes in any bodily fluid, or CSF WBC $\geq 50/\mu$ L, or CSF WBC > 20 and $< 50/\mu$ L and increased in relation to previous value(s), or a change in treatment.

Table 6 – Study Schedule

Final version of protocol	June 2012		
Study treatments available	June 2012		
First patient first visit	October 2012		
Duration of enrolment period	24 months		
Duration of follow-up period	18 months (primary endpoint) – 24 months (follow-up)		
Last patient last visit	September 2016 (primary endpoint) – March 2017 (24-month follow-up)		
Final study report	December 2016 (primary endpoint) – June 2017 (follow-up)		

Table 7 – Expected Enrolment Rates (actual rates up to Q2 2013)

	Actual Enrolment	2015	
Study Sites	Q3 2012 – Q4 2014	Q1	Total per site
01 Bandundu	47	5	52
02 Vanga	61	5	66
03 Masi Manimba	82	4	86
04 Dipumba	51	3	54
05 Dingila	32	0	32
06 Batangafo	12	0	12
07 Mushie	19	4	23
08 Katanda	19	4	23
09 Isangi	31	4	35
10 Bagata	3	4	7
Cumulative Total	357	33	390

The forecast may be revised if new investigational sites are added.

[figure not shown]
Table 8 – Overall Organisation of the Study

Target countries	countries Democratic Republic of the Congo (RDC), Central African Repu (CAR)				
Target enrolment rate		Screened	Randomised		
	TOTAL	592	390		
Number of sites	At least 6 sites				
Number of patients	Up to 140 patients per site				
randomised per site					
Participation of a	An independent steering committee (ISC or DSMB) will be appointed				
DSMB	to look after safety issues.				
Partners	Swiss Tropical and Public Health Institute, Basel, Switzerland Study Coordination Monitoring Logistics (Swiss TPH/DNDi Kinshasa) Ministry of Health, Kinshasa, DRC Primary Investigator PNLHAT, Kinshasa, DRC Management of Investigator team Coordination of supplies MSF Technical support Logistical support				
Other material required for study					

Appendix 5 - Figures

Figure 3 – Statistical Power of the Study

Power of the study depending on the actual difference between the success rates and assuming a success rate of 94% for NECT

The power is improved if the efficacy of NECT is greater than 94%.

The power refers to the probability that the 95% confidence interval of the difference in success rates will exclude the margin of the chosen limit of an unacceptable difference.

The interval between an acceptable difference and an unacceptable difference, as reported by those who responded to the survey, is a "grey area" or a zone of uncertainty.

The Sponsor objective is to have at least an 80% chance of being significant if the actual difference is 5% in favour of NECT, and a very limited chance (1.45% = exact power = exact one-sided type-I error) of being significant if the actual difference is 13%.

Figure 4 – Acceptable and Unacceptable Limits of the Difference in Efficacy at the Testof-Cure Visit

Responses to two questions:

- what is the acceptable margin of difference in efficacy between an oral drug and NECT?
- what is the unacceptable margin of difference in efficacy between the two treatments?

[figure not shown]

Figure 5 – Failure Rate at each Timepoint by Compound

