The primary analysis will be performed using a Blackwelder noninferiority test, based on the difference in the success rates at the Test-of-Cure Visit at 18 months with the maximum margin of noninferiority set at 13%.

The interim primary analysis will be performed using the same test, but with the timepoint of 12 months.

Sample Size

The sample size, initially calculated at 510 patients with statistical power of 87.9% has been reduced to 390 patients in total, with 260 patients in the fexinidazole group and 130 patients in the NECT group. Thus, the overall power is 80% if the actual success rate for NECT is 94% and 89% for fexinidazole.

Futility Analyses

Futility analyses will be performed in order to inform decisions about possible study discontinuation, based on pre-determined stopping rules. The aim is to limit the number of patients exposed to the investigational product in the event that the latter should prove to have limited efficacy.

Of note: data handling and data review will be performed in a blinded manner.

Interim Secondary Analyses

In the interim analyses, the success rate for NECT and for fexinidazole will be calculated on patients who have reached the 18-month follow-up visit and the rates will be compared to those calculated at the 12-month visit in the same patients.

The time course of the success rate will be analysed on the data available, using the same approach as for the final secondary analysis.

1. Background and Study Rational

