9.1. Sample Size Determination

The calculation of the sample size has been revised. The total size of the sample is now calculated to be 390 patients, instead of 510, with the same 2:1 allocation ratio, i.e. 260 patients in the fexinidazole group and 130 patients in the NECT group. If the expected success rates are 94% with NECT and 89% with fexinidazole³ then the power of the final analysis is 80% with an acceptability ("non-inferiority") margin of 13%. The calculations were made for a one-sided type-1 error of 0.025.

No provision will be made for patients lost to follow-up since the missing outcome will be imputed, except for patients in areas of armed conflict (see Section 8.3).

³ The observed response rate for NECT was as high as 0.97 in the per protocol population and 0.965 in the ITT population (43). However, the definition of success was not the same as in this protocol, and the success rate for NECT would have been 0.95 or 0.94 if the same definition had been used. If fexinidazole has the same true success rate as NECT, and is equal to 0.95 or 0.94, then the power of the study will be greater than 99%. However, NECT is a co-administration of two drugs and there is no reason to expect fexinidazole to be more effective than effornithine alone. Available data show that the success rate with effornithine depends on the project and ranges between 0.89 and 0.90. If the expectations are 0.90 for fexinidazole and 0.95 for NECT, the exact power of the final primary analysis is 91.6%.

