9.8. Efficacy Analysis

9.8.1. Primary Efficacy Analysis

Primary Efficacy Endpoint

The primary efficacy endpoint is the outcome at 18 months. Outcome will be considered as a success if there is no evidence of trypanosomes in any bodily fluid and if the CSF WBC is $\leq 20/\mu$ L. Death and use of rescue treatment will be considered as a relapse, i.e. a failure. A patient who attends the 18-month visit or who is found again after an active search, who refused to undergo lumbar puncture but who has no signs or symptoms of HAT, and for whom the outcome was assessed as favourable at the latest assessment will be considered as a probable cure, i.e. a success, unless signs of relapse are detected on any assessment up to 24 months.

Primary Assessment Criterion

The primary assessment criterion is the success rate at 18 months.

Primary Test

The primary test is the Blackwelder non-inferiority test, based on the difference in the success rates and a margin of 13% (see Margin for "Acceptable Difference"; p 63).

Primary Measure of Size of Effect

The size of the treatment effect will be measured by the excess rate of success. The excess success rate is equal to the difference in the success rates between the two groups: size of effect = p_{fexi} - p_{NECT} . A negative success rate corresponds to a treatment effect in favour of NECT.

Margin for "Acceptable Difference"

The margin for an "acceptable difference" is set at $13\%^6$.

⁶ A survey was carried out by e-mail in the small population of local and international physicians who are experienced in treating patients with HAT, in order to assess the limit of an acceptable difference and the limit of an unacceptable difference in efficacy between an oral drug and NECT. Between the two limits, there is an "uncertainty zone". The median response for an unacceptable difference was 17% and the median response for an acceptable difference was 9%. A margin of 13% was chosen and is equal to the first tertile of the distribution of an unacceptable difference. It means that the unacceptable limit was above 13% for 2/3 of respondents, i.e. for 6/19 respondents, the unacceptable limit was below 13% and, for 12/19, the limit was above 13%. The margin of 13% is also at the mid-point between the median of an acceptable difference (9%) according to respondents and the median of an unacceptable difference (17%) for the same respondents (see results of the survey in Figure 4; p 108).

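### The 1.45% type-I error printed with Figure 3 does not belong to the test that gives 80% power at 390 patients; it and footnote 3's 91.6% look carried over from the 510-patient design

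*Protocol*

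**What the plan says.** Section 9.1 sets the current design: "260 patients in the fexinidazole group and 130 patients in the NECT group". It continues "If the expected success rates are 94% with NECT and 89% with fexinidazole", "then the power of the final analysis is 80" per cent, with a margin of 13%, and adds "The calculations were made for a one-sided type-1 error of 0.025". The Sample Size entry of the Protocol Summary repeats the 80% and records that the size was "initially calculated at 510 patients with statistical power of 87.9" per cent before it was reduced to 390.

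Section 9.8.1 names a single primary test: "The primary test is the Blackwelder non-inferiority test, based on the difference in the success rates and a margin of 13" per cent.

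The text under Figure 3 (Appendix 5) plots power "assuming a success rate of 94% for NECT" and defines significance as the 95% confidence interval excluding the margin. It gives the sponsor's objective as at least 80% power at a true 5-point deficit, together with "a very limited chance (1.45% = exact power = exact one-sided type-I error) of being significant if the actual difference is 13" per cent. It names no sample size.

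Footnote 3 to Section 9.1 gives 91.6% as the exact power of the final primary analysis for 90% against 95%. Section 9.11 says a Pocock approach will set the significance thresholds of both the interim and the final analysis, but gives no numerical level.

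**The concern.** A reader of the current version takes the 80% and the 1.45% as two properties of the same primary test at the same 390 patients. For a fixed sample size the two are tied together: a stricter test lowers both. An exact error of 1.45% is well below the nominal 2.5%, so it implies a conservative test, and the 80% has to be checked against that same test.

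At stake is how Figure 3 is read. The 1.45% reassures the reader that a drug truly at the margin would almost never pass. If the test behind the 80% is used, that chance is 2.32 / 1.45 = 1.6 times as large. If the test behind the 1.45% is used, the trial falls short of its stated power.

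**Working it through.** **Inputs.** 260/130 (Section 9.1); the superseded 510 split 2:1 as 340/170 (Protocol Summary); true rates of fexinidazole 89% and NECT 94% for power; 81% and 94% for the error (94% minus the 13-point margin); 90% and 95% for footnote 3; margin 0.13; one-sided 0.025, critical value 1.960.

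**Step 1: reproduce the 80%.** Unpooled normal formula, no continuity correction:

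- Variance = 0.89 × 0.11 / 260 + 0.94 × 0.06 / 130 = 0.0003765 + 0.0004338 = 0.0008104, so SE = 0.02847.
- Distance from the margin = 0.13 − 0.05 = 0.08, and 0.08 / 0.02847 = 2.810.
- Power = Φ(2.810 − 1.960) = Φ(0.850) = 80.2%.

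The stated 80% at 390 is therefore the uncorrected asymptotic figure.

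**Step 2: exact properties at 260/130 and 340/170.** For every pair of success counts, compute z = (p_fexi − p_NECT + 0.13 − c) / SE, with SE from the observed rates. Here c = 0 (uncorrected) or c = 0.5 × (1/n_fexi + 1/n_NECT) (corrected; 0.00577 at 260/130). The exact rejection probability is the sum of the binomial probabilities of all pairs with z ≥ 1.960.

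| Patients | Test | Error, 81 vs 94 | Power, 89 vs 94 | Power, 90 vs 95 |
|---|---|---|---|---|
| 390 | uncorrected | 2.32% | 82.3% | 86.8% |
| 390 | uncorrected, n−1 variances | 2.13% | 82.2% | 86.7% |
| 390 | corrected (n or n−1) | 1.42% | 76.0% | 81.3% |
| 510 | uncorrected (n or n−1) | 2.16% | 90.9% | 94.1% |
| 510 | corrected, n variances | 1.52% | 87.8% | 91.6% |
| 510 | corrected, n−1 variances | 1.45% | 87.3% | 91.4% |
| *Printed* | | *1.45%* | *80% (390); 87.9% (510)* | *91.6%* |

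**Step 3: compare.** At 390 no row gives 1.45% together with 80%. Other statistics held to an error near 1.45% do not help: Farrington-Manning (1.46%) has 75.2% to 75.9% power, a Newcombe interval (1.46%) has 75.9%, and the uncorrected test with a stricter cut-off (1.44%) has 77.6%. The corrected test reaches 80% only between 420 patients (79.8%) and 426 patients (80.3%).

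At 510 the corrected test comes close to all three older figures: 1.45% to 1.52% against the printed 1.45%, 87.3% to 87.8% against 87.9%, and 91.4% to 91.6% against 91.6%.

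**Step 4: threshold of the final analysis.** Section 9.11 gives no level. Assuming two equally spaced looks, the Pocock one-sided level is about 0.0147 (critical value 2.178). At 260/130 the exact final-look pairs are then 1.2% error with 75.7% power (uncorrected), or 0.7% with 68.6% (corrected). Power over both looks, if they tested the same endpoint, is about 76% by the normal approximation without correction.

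**The case against.** **Figure 3 is not self-contradictory when read alone.** This stands. Its text names no sample size and words the 80% as an objective. At 510 the corrected test meets both statements, with an error of 1.45% and power of 87.3%. A reader might infer that the figure contradicts itself, but the documents do not support that. The conflict arises because Section 9.1 and the Protocol Summary state 80% as the power at 390, while the figure text stands in the same version with no note that it refers to 510.

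**Two different statistics.** A reader might also infer that the sponsor mixed two test versions for the 390-patient design. That is not shown. The simpler explanation is that the 1.45% was not recalculated, and the 91.6% in footnote 3 points the same way.

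**The 1.45% could be the Pocock level.** It is numerically close to 0.0147, but the figure text presents it as an exact error at a true 13-point difference and refers to a 95% interval. That reading would not restore 80% in any case (Step 4).

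**Test details belong in the SAP.** This is fair. The protocol's silence on continuity correction is not an error in itself. The point is only that the printed figures must come from one version of the test.

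**Little depends on it.** This largely stands. No decision rule uses the 1.45%, and Section 9.8.1 gives the effect estimate and its confidence interval precedence over the test result.

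**Conclusion.** The point holds as an error in printed figures, of minor weight. At 260/130 and one-sided 0.025, the test that reproduces the 80% has an exact error of 2.3% (2.1% with n−1 variances), and the corrected test with an error near 1.45% has 76.0% power. The 91.6% in footnote 3 is too high for 390 patients by about 10 points (corrected) or 5 points (uncorrected).

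It would be wrong to conclude that error control is at risk: both Blackwelder versions stay below 2.5%.

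That the figures are left over from the 510-patient design is inferred from the numerical match; the documents do not say so. The recomputed figures assume the unpooled Blackwelder statistic and the true rates given in the Protocol. The Pocock figures also assume two equally spaced looks.

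**What to change.** Recompute, all at 260/130, from one named version of the Blackwelder test and at the Pocock-adjusted threshold used in the final analysis:

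- the type-I error and power given with Figure 3;
- the 80% in Section 9.1 and in the Protocol Summary;
- the 91.6% in footnote 3.

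State the sample size, test version and significance level beside Figure 3.

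For orientation, the error/power pairs at an unadjusted 0.025 are 2.3% / 82% (uncorrected) or 1.4% / 76% (corrected). At an assumed Pocock level of about 0.0147 the final-look pairs are about 1.2% / 76% or 0.7% / 69%. The unadjusted pairs should not be printed as properties of the final analysis if the Pocock threshold applies.

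The cost is a recalculation and restated figures, some of them less favourable than those now printed. Patient numbers, data collection and the primary test need not change.
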